2.2. Sample Size and Power Considerations

During the study design stage, a sample size of 65 participants per arm was calculated to obtain 90% power to detect a mean difference in average TNSS (2 to 6 hours) of 1.61 (30% reduction from placebo) between REGN5713-5714-5715 (mean TNSS = 3.74) and placebo (mean TNSS = 5.35), assuming a common standard deviation of 2.8. Assuming 10% dropout, approximately 73 participants per arm will be required to detect a difference of 1.61 in mean TNSS between REGN5713-5714-5715 (3-mAb) and placebo with a minimum detectable difference of 1.0 (~19% reduction from placebo in mean TNSS). Across all 4 treatment arms, the proposed sample size is approximately 300 participants.

This sample size is calculated at a 2-sided significance level of 5% using a 2-sample t-test. Estimates of mean in placebo and variability of the TNSS are based on birch tree SLIT-tablet data (Couroux P, 2019), and a 30% treatment effect relative to placebo is in line with what was observed in the phase 1b POC study for REGN5713-5714-5715.

Pollen related allergy trials are dependent on timing of the specific pollen seasons. As such, enrollment is affected by pollen season start dates. A sample size of 50 participants per arm gives approximately 80% power to detect a mean difference in average TNSS (2 to 6 hours) using the same assumptions. This study is powered to detect differences between REGN5713-5714-5715 900 mg and placebo on the primary endpoint of the mean of TNSS during a birch pollen EEU challenge (2 to 6 hours) at day 29 in Part A.

3. ANALYSIS SETS

The following defines the set(s) of subjects whose data will be used for statistical analyses.

3.1. The Full Analysis Set (FAS)

The efficacy endpoints in Part A will be analyzed using the Full Analysis Set (FAS), which consists of all randomized participants. The efficacy analysis set is based on the treatment allocated (as randomized).

The efficacy endpoints in Part B will be analyzed using the FAS - B, which consists of participants who receive study drug in Part B.

3.2. Modified Intent-to-Treat Set (mITT)

The mITT includes all randomized participants that were eligible to complete their day 29 EEU challenge (visit 6) prior to the start of local birch pollen season. This mITT analysis set excludes any participants that were unable to complete their day 29 EEU challenge prior to their local birch season start (due to earlier than expected birch season start).

3.3. Part A Completers Set (CS-A)

The CS-A includes all randomized participants who complete all out-of-season birch EEU challenges in Part A (visit 6, visit 8, and visit 9). CS-A will be used to assess the durability of response in part A and evaluate within-participant changes over time in Part A.

3.4. The Safety Analysis Set (SAF)

The safety analysis will be based on the safety analysis set (SAF), defined as all randomized participants who receive any study drug, regardless of the amount of treatment administered. The SAF is based on the treatment received (as treated). As-treated is defined as when a patient receives at least one dose of any amount of study drug, in case of interrupted dosing. The patient will be regarded as treated with 3-mAb cocktail study drug REGN5713-5714-5715 if the patient receives at least 1 dose of the 3-mAb cocktail. Similarly, if a patient receives at least one dose of the 2-mAb cocktail, but no doses of REGN5714, the patient will be considered treated with REGN5713-5715. If a patient receives at least one dose of the single mAb REGN5715 but no doses of REGN5713 or REGN5714, then the patient will be considered treated with REGN5715. If the patient receives no REGN5713, REGN5714, or REGN5715, the patient is considered as treated with placebo.

3.5. Immunogenicity Analysis Sets

3.5.1. ADA Analysis Set (AAS)

The ADA analysis sets (AAS) are defined for each study drug separately and include all treated participants who received any amount of study drug (active or placebo [SAF]) and had at least one non-missing ADA result following the first dose of the respective study drug or placebo. The ADA analysis set is based on the actual treatment received (as treated) rather than as randomized.

3.6. Pharmacokinetic Analysis Set (PKAS)

The PK analysis set (PKAS) includes all participants who received any active drug and who had a at least 1 non-missing serum drug concentration following a single dose of study drug. Participants will be analyzed according to the treatment actually received rather than as randomized.

GENERAL STATISTICAL ANALYSIS CONSIDERATIONS 4.

Unless otherwise stated, the following conventions will be applied when presenting summary level statistics for data.

Date: May 31, 2023

Continuous variables will be summarized within each treatment group, presenting the following summary statistics. The sample size (i.e. number of observations with an available value of the variable), average, sample standard deviation, median, minimum, maximum, 1st quartile and 3rd quartile.

Categorical data will be summarized within each treatment group by frequency (i.e., total number of observations within each level of the categorical variable in a given treatment group). All levels of the categorical variable will be included. If there are observations where the level of the categorical variable is missing, a separate category titled "Missing" will be created. For categorical variables that are ordinal in nature, the order in which the levels of the categories are displayed will be consistent with the natural ordering of the category levels. Percentages will also be calculated for each level of the categorical variables with respect to the total sample size for the respective treatment arm.

5. PATIENT DISPOSITION

5.1. Screening Dispositions

The number of enrolled participants (i.e. participants who signed the informed consent form (ICF)) who are randomized (i.e. assigned a randomization number in the IWRS system) and screen-fail will be presented. Participants who screen-fail will be broken out by screen-fail reason. If applicable, the number of participants who are improperly randomized (i.e. did not meet study eligibility criteria yet were assigned a randomization number in the IWRS system) will also be displayed. The corresponding percentages with respect to the total number of enrolled participants will also be presented.

5.2. Treatment Period Dispositions

A patient is considered to have completed the study treatment period if they make it to the Endorf-Study Visit (visit 15/day 253). The disposition of all randomized participants during the study treatment period will be displayed by treatment group.

The following summaries will be provided for each treatment group and total (unless otherwise specified):

- Study drug administration
- The total number of participants in each analysis set
- The number of participants who complete the study treatment period
- Duration of study treatment period
- The number of participants completing each visit
- The number of participants who withdraw from the study treatment period. This number will be further broken out by reason for early withdrawal and whether the early termination/ withdrawal was prior to or after the start of the local BPS.

DEMOGRAPHICS AND BASELINE CHARACTERISTICS 6.

6.1. **Demographics**

The following demographic variables will be summarized by treatment group and overall:

- Age at screening (years) as a continuous variable
- Age categories (years, 18 to <50, >=50)
- Sex (Male, Female)
- Race (American Indian or Alaskan Native, Asian, Black or African American, Native Hawaiian or Other Pacific Islander, White, Not Reported)

Date: May 31, 2023

- Ethnicity (Hispanic or Latino, Not Hispanic or Latino, Not Reported)
- Weight (kg)
- Height (cm)
- Body mass index (BMI) (kg/m2)
- EEU location (Cliantha, Kingston)
- Site location (Cliantha, Kingston, CSAC)

6.2. **Baseline Disease Characteristics**

The following disease characteristics will be summarized by treatment group and overall:

- Birch EEU Mean TNSS (2 to 6 hours), Mean TOSS (2 to 6 hours), Mean TSS (2 to 6 hours) at Visit 2
- Oak EEU Mean TNSS (2 to 6 hours), Mean TOSS (2 to 6 hours), Mean TSS (2 to 6 hours) at Visit 3 [only for oak-allergic participants, i.e., those who developed a TNSS of at least 6 out of 12 at 2 or more timepoints during the screening oak EEU at visit 3]
- Screening and randomization FEV1 (L and percent predicted)
- Baseline history for allergic disease, including duration of disease [e.g., allergic rhinitis, allergic conjunctivitis, asthma and pollen food allergy, and prior SIT] (as recorded in CRF)
- SPT mean wheal diameter for birch allergens, birch-related allergens, and unrelated allergens (mm)
- Serum total IgE (kU/L)
- Serum allergen-specific IgE for birch allergens, birch-related allergens, and unrelated allergens (kU/L)
- Serum allergen-specific birch IgE (<17.5 kUa/L; ≥17.5 kUa/L)

- Sensitization to allergens by either sIgE or by SPT
- Sensitization status by sIgE or by SPT (sensitized to birch and related allergens only; sensitized to unrelated trees; sensitized to non-tree pollens; sensitized to indoor perennial allergens)
- Serum Bet v 1 sIgG, birch sIgG, and oak sIgG (if data are available)

Note: Refer to Section 14.5 for allergen definitions.

6.3. Medical History

Patient medical histories will be coded using the Medical Dictionary for Regulatory Activities (MedDRA®). The frequency and percentage of each medical history will be summarized by SOC and PT for each treatment arm, and overall using the FAS.

7. EFFICACY/PHARMACODYNAMIC DATA

7.1. Description of Efficacy/Pharmacodynamic Data

EEU Data (symptom scores recorded during the 6 hour EEU challenges):

Nasal and ocular symptom data will be collected during EEU visits that occur during the screening period, out-of-season efficacy period, in-season efficacy period, and at end-of-season. The methodology for collecting and scoring the nasal and ocular symptom data in the EEU is consistent across all periods stated previously.

• TNSS (2 to 6 hours):

Instantaneous TNSS measures nasal symptom severity at the time point of assessment. In the EEU, instantaneous TNSS is recorded using an e-diary prior to start of pollen exposure and then approximately every 20 min during the 6-hour EEU pollen exposure.

The instantaneous TNSS score ranges from 0 to 12 and is based on assessment of 4 nasal symptoms graded on a Likert scale ranging from 0 (none) to 3 (severe) for nasal congestion, itching, and runny nose, and sneezing. Higher score indicates worse symptoms.

The mean TNSS (2-6 hours) is calculated as an average of the observed instantaneous TNSS scores during the 12 timepoints from hour 2 to 6 during the EEU session (details in Section 11.4).

• TOSS (2 to 6 hours):

Instantaneous TOSS measures ocular symptom severity at the time point of assessment. In the EEU, instantaneous TOSS is recorded using an e-diary prior to start of pollen exposure and then approximately every 20 min during the 6-hour EEU pollen exposure.

The intantaenous TOSS score ranges from 0 to 6 and is based on 2 groups of eye symptoms: itching/redness/gritty feeling and tearing/watering. Each of the 2 symptom groups is graded on a Likert scale ranging from 0 (none) to 3 (severe). Higher score indicates worse symptoms.

The mean TOSS (2-6 hours) is calculated as an average of the observed instantaneous TOSS scores during the 12 timepoints from hour 2 to 6 during the EEU session (details in Section 11.4).

• TSS (2 to 6 hours) (calculated):

The mean TSS (2 to 6 hours) is calculated as an average of the sum of observed instantaneous TNSS and instantaneous TOSS scores during the 12 timepoints from hour 2 to 6 during the EEU session (details in Section 11.4). The mean TSS (2 to 6 hours) score ranges from 0 to 18 with higher scores indicating worse symptoms.

Note: Baseline data are obtained from the screening baseline EEU challenge for birch (visit 2) and oak (visit 3).

Daily scores:

Daily nasal, ocular, and medication data will be collected during pre-treatment baseline, pre-season baseline, and then starting at visit 10 until end of the study. The methodology for collecting and scoring the daily nasal, ocular, and medication data is consistent across all periods stated previously.

• TNSS (daily)

Reflective TNSS measures nasal symptom severity over the past 24 hours and is recorded before the participant goes to bed for the night. It is recorded daily using an e-diary in the Part B. All daily TNSS scores during the season after the dose #2 will be used to calculate the average TNSS, except for the day of and one day following EEU challenge in Part B.

• TOSS (daily)

Reflective TOSS is similar to the reflective TNSS defined above.

• TSS (calculated)

The TSS is calculated by adding the TNSS and TOSS together, with scores ranging between 0 and 18. Higher score indicates worse symptoms.

• DMS (daily)

To calculate the DMS, participants will be asked to record their daily rescue medication use using an e-diary before going to bed for the night, including which medications and the amount of these pre-specified medications. This information will be used to calculate the DMS for the following medications or the approved in-class equivalents, as follows:

- Desloratadine 5 mg 6 points/dose; maximum daily score 6 points
- Olopatadine 1 mg/mL each drop 1.5 points/drop; maximum daily score 6 points
- Mometasone furoate 50 ug/dose 2.0 points/spray; maximum daily score 8 points

The maximum DMS score is 20 (Calderon, 2014). DMS is recorded using an e-diary from visit 10 to visit 15, in addition to an approximately 2-week period during screening. After completion of the EEU challenges, use of allergy medicines will be recorded in the e-diary until approximately 24 hours after the start of the EEU challenges. All daily e-diary scores during the season after dose #2 will be used to calculate the average, except for the day of and one day following EEU challenge in Part B.

• Daily CSMS (calculated)

The CSMS is calculated by adding the DMS and TSS together, with scores ranging between 0 and 38. For each participant, an average of the daily symptom and medication scores is calculated during their local BPS.

Note: Daily TNSS, TOSS, DMS, CSMS scores on the day of and the day after an EEU challenge will not be used as part of the field data calculations (to avoid any potential overlap of symptoms related to the EEU).

Standardized RQLQ(S) for Ages 12+

The RQLQ(S) is a self-administered questionnaire to measure health-related quality of life in those 12 years of age and above, as a result of perennial or seasonal allergic rhinitis.

There are 28 items on the RQLQ(S) in 7 domains: activity limitation, sleep problems, nasal symptoms, eye symptoms, non-nasal/eye symptoms, practical problems, and emotional function. The RQLQ(S) responses are based on a 7-point Likert scale with responses ranging from 0 (not troubled) to 6 (extremely troubled). The overall RQLQ(S) score is the mean of all 28 responses and the individual domain scores are the means of the items in those domains. Higher scores indicated more health-related quality of life impairment (lower scores are better).

Questionnaire is administered weekly (starting at visit 10 to the end of the study) and an average of the questionnaires during the BPS will be calculated.

Titrated Skin Prick Testing for European White Birch, White Alder, and Red Oak Allergens

The titrated SPT will be performed with 6 serial dilutions for three allergen extracts (European White Birch, White Alder, and Red Oak), a negative control, and a histamine positive control. Serial dilutions for each of the allergens will be created using diagnostic allergen extract (1:20 weight/volume concentration). The 6 dilutions for the titrated SPT will be created as sequential 50% dilutions to yield 1:40 w/v, 1:80 w/v, 1:160 w/v, 1:320 w/v, 1:640 w/v and 1:1280 w/v concentrations for each allergen. The *mean wheal diameters* for the 6 serial dilutions for each allergen will be used in the calculation of the area under the curve of the titrated SPT.

The AUC of the titrated SPT *mean wheal diameters* will be derived using the trapezoidal rule. For each patient, the AUC will be calculated for the *mean wheal diameter* calculated over the titrated concentrations of birch allergen on a log scale. For example, the AUC will be calculated using the formula (Orengo J, 2018):

$$AUC_{\text{[Titrated SPT MWD]}} = \left[\sum_{i=1}^{5} (l_{i+1} - l_i) * (D_{i+1} + D_i)/2 \right] / (l_6 - l_1)$$

Where

- D_i is the mean wheal diameter (in mm) obtained at concentration c_i
- $l_i = \log(c_i)$, where c_i is the concentration (in w/v units) for which D_i is measured, such as $c_1 = 1:40$, $c_2 = 1:80$, $c_3 = 1:160$, $c_4 = 1:320$, $c_5 = 1:640$, $c_6 = 1:1280$.

Note: c_0 (1:20 w/v concentration of the diagnostic allergen extract) will not be used to calculated the AUC of the titrated SPT mean wheal diameters. Histamine phosphate 1 mg/ml for SPT will be used as the positive control. All normalized SPT values will be considered positive if >=3mm greater than the negative control

Definition Pollen Sites and Pollen Seasons

Pollen Sites

Pollen sites, based on local pollen counter locations, will be used to define the start and end of the local pollen season at the patient level.

Birch pollen season

Local pollen count data will be used to determine the start and end of the BPS for participants at each pollen site. The start of the BPS is defined as the first of 3 consecutive days with a pollen count of 10 grains/m3 or greater. The end of the BPS is defined as the last day of the last occurrence of 3 consecutive days with a pollen count of 10 grains/m3 or greater. Additionally, a threshold using 30 grains/m3 for defining the birch season may be used (higher threshold may be more consistent in predicting the onset of symptoms in birch allergic participants) (Caillaud, 2023; Taudorf, 1988; Biedermann, 2019).

Peak birch pollen season

Peak BPS is defined as the 15 consecutive days within the BPS with the highest 15-day moving average pollen count.

Oak Pollen season

The start of the OPS is defined as the first of 3 consecutive days with a pollen count of 10 grains/m3 or greater. The end of the OPS is defined as the last day of the last occurrence of 3 consecutive days with a pollen count of 10 grains/m3 or greater. The peak OPS is defined similarly to peak BPS, which is the 15 consecutive days within the OPS with the highest 15-day moving average pollen count.

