- To determine the efficacy of the anti-Bet v 1 monoclonal antibodies (dose #2) in the reduction of allergic symptoms during the birch pollen season and peak birch pollen season in participants receiving REGN5713-5714-5715 versus placebo, and REGN5715 versus placebo (Part B)

• To determine the efficacy of the anti-Bet v 1 monoclonal antibodies (dose #2) in the reduction of skin test reactivity from pre-treatment baseline by inhibiting a wheal response to a titrated skin prick test with birch and related allergens (eg, alder, oak) after the natural birch pollen season in participants who receive REGN5713-5714-5715 versus placebo, REGN5713-5715 versus placebo, and REGN5715 versus placebo (Part B)

Secondary Endpoints

- The proportions of participants achieving different degrees of responses in the birch (and related allergens) titrated SPT mean wheal diameter AUC will be compared across different response thresholds at days 29, 57, and 85
- The mean of symptom scores during the peak-season birch allergen EEU challenge
 - o TNSS (2 to 6 hours)
 - o TOSS (2 to 6 hours)
 - o TSS (2 to 6 hours)
- The daily symptom and medication scores, averaged during the BPS and peak BPS
 - o CSMS, TSS, TNSS, TOSS, and DMS, averaged during the BPS
 - o CSMS, TSS, TNSS, TOSS, and DMS, averaged during the peak BPS
- The change and percent change from baseline in the symptom and medication scores, averaged during the BPS and peak BPS
 - o CSMS, TSS, TNSS, TOSS, and DMS, averaged during the BPS
 - o CSMS, TSS, TNSS, TOSS, and DMS, averaged during the peak BPS
- The change and percent change from pre-treatment baseline to end-of-season and end-of-study (EOS) visits in the birch (and related allergens) titrated SPT mean wheal diameter AUC

Secondary Objectives	Secondary Endpoints
To assess health-related quality of life during the BPS and peak BPS in participants who receive REGN5713-5714-5715 versus placebo, REGN5713-5715 versus placebo, and REGN5715 versus placebo	 The mean of the total Rhinoconjunctivitis Quality of Life Questionnaire (RQLQ[S]) score during BPS and peak BPS RQLQ(S), averaged during the BPS and peak BPS Change and percent change from baseline in the average RQLQ(S) during the BPS and peak BPS

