- At minimum, a 12-week interval between doses #1 and #2 is required. Dose #2 is intended to be given within 3 weeks prior to an anticipated birch season and a dosing stop date is defined within approximately 1 week after the concurrent birch pollen season start. Some participants may receive dose #2 after start of the birch pollen season. Some participants that are enrolled later in the study may not receive dose #2 if they do not meet the minimum 12-week interval prior to the defined dosing stop date.
- In-season peak EEU challenge at visit 13 is intended to be conducted in the birch season during the approximate anticipated peak season (after dose #2 for those expected to receive it)
- End-of-season EEU challenge (visit 14) is expected to be performed after the end of the local birch season. (Note: Participants that are highly symptomatic to grass pollens or unable to wash out allergy rescue medications may not perform this EEU challenge.)

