In addition, some in-season efficacy analyses in Part B may be performed including participants with available in-season data irrespective of whether they received dose 2.

More details concerning other secondary endpoints, see Section 14.1.

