7.2.2.1. Estimand Framework for Secondary Endpoints

The intercurrent events, strategies, and the corresponding missing data handling approaches for the secondary estimands of interest for the secondary endpoints are provided in detail in Table 3:

Table 3: Summary of Estimands for Secondary Endpoints

	Estimand			
Endpoint Category	Endpoint	Population	Intercurrent event(s) handling strategy and missing data handling	Population-level summary
Secondary endpoint - Continuous	Titrated SPT MWD	FAS ¹	If the antihistamines are not withheld before the titrated SPT, the post-randomized data will be assigned by worst observation (including baseline) before the collection of the assessment from the same participant (composite strategy). If all dilutions are missing due to any reason, e.g., early start of BPS, then the averaged value will be imputed using multiple imputation (MI).	ANCOVA model with treatment group and stratification factors as fixed effect and the baseline tSPT as a covariate.
	EEU symptom scores ³ in Part B	FAS-B	Same manner as the primary endpoint with the following exception: If systemic steroids, biologics or immune therapeutics impacting type 2 allergic disease are used due to birch pollen related symptoms ⁶ prior to the EEU challenge, data will be set to mean score from 2 to 6 hours in the baseline EEU (BOCF, composite strategy).	Same manner as the primary endpoint
	Field symptom scores ⁴ in BPS ⁵ and peak BPS	FAS-B	 The intercurrent events will be handled as follows: If Systemic steroids, Biologics or immune therapeutics impacting type 2 allergic disease are used due to birch pollen related symptoms⁶, data will be set to mean score from the other participants in the same treatment group (composite strategy). If due to any other reason, data after the use of medication will be set to missing (hypothetical strategy). Study provided anti-allergy rescue treatment taken during the study: all available data will be utilized (treatment policy) Data during travel periods with no exposure to birch pollen will be set to missing and other observed data during exposure to birch pollen will be used to calculate the mean scores (while on treatment policy) 	ANCOVA model with treatment group, stratification factors as fixed effect, average pollen count during local BPS and the corresponding pre-treatment baseline symptom scores as covariate.

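### The SAP averages in-season diary scores only over days after dose #2, an unlisted narrowing of the season-average endpoint that gives participants without dose #2 no TNSS, TOSS, TSS or DMS average

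*SAP*

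**What the plan says.** Protocol 2.2 defines the field endpoint as "The daily symptom and medication scores, averaged during the BPS and peak BPS", for CSMS, TSS, TNSS, TOSS and DMS. SAP 7.1.2 keeps that definition. Neither mentions a limit tied to dose #2.

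The derivation rules in SAP 7.1 (Daily scores) are narrower:

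- TNSS: "All daily TNSS scores during the season after the dose #2 will be used to calculate the average TNSS", leaving out the day of a Part B EEU challenge and the day after.
- TOSS: "Reflective TOSS is similar to the reflective TNSS defined above".
- DMS paragraph: "All daily e-diary scores during the season after dose #2 will be used to calculate the average", with the same EEU exclusion.
- CSMS paragraph: "For each participant, an average of the daily symptom and medication scores is calculated during their local BPS", with no reference to dose #2.

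SAP 2.1 says "Some participants may receive dose #2 after start of the birch pollen season", sets a dosing stop date roughly one week into the season, and notes that some late enrollees may not be redosed at all. SAP 3.1 restricts the main Part B set, FAS-B, to participants who receive study drug in Part B. SAP 7.2.2 allows some in-season analyses of participants with available data "irrespective of whether they received dose 2". For field scores in both BPS and peak BPS, SAP Table 3 specifies one pollen covariate, the "average pollen count during local BPS". SAP 1.4, which lists departures from the protocol's statistical section, does not mention the averaging window.

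**The concern.** The endpoint is a season average; the derivation is an average over part of the season for anyone dosed after it began. A change of window is a change of endpoint, and SAP 1.4 records smaller things, such as a renamed analysis set. Because the CSMS paragraph omits the restriction that precedes it, two programmers could derive different averages from the same diary.

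The second issue is selection. FAS-B is defined by an event after randomisation, receipt of dose #2. Participants who miss that dose are encouraged to stay in the study (Protocol 5.1), so their diary data may exist. The only stated route for bringing them back is the optional analysis in SAP 7.2.2. A rule that counts only days after dose #2 leaves them with no days to average.

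The third is smaller. The peak-BPS scores cover 15 days, but their pollen covariate covers the whole season, so it measures exposure partly on days that do not contribute to the score.

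**Working it through.** The documents give no figure for this, so there is nothing to reproduce. The check compares the texts and sizes the gap.

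**Inputs.**
- d, days from season start to dose #2: 0 if dosed before the season; about 7 at the latest (SAP 2.1).
- L, season length: Protocol 3.3 calls about 2 months typical, taken as 60 days. Shorter seasons of 21, 30 and 45 days are assumptions.
- Peak BPS: 15 days (SAP 7.1).
- EEU-day and travel-day exclusions are ignored.

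**1. Share of season days dropped, d/L.**
- d = 0: none; the two windows coincide.
- d = 7: 7/21 = 33%; 7/30 = 23%; 7/45 = 16%; 7/60 = 12%.

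**2. Peak days dropped.** At most 7/15 = 47%, and only if the peak begins on the first season day. If the peak starts after dose #2, none.

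**3. Effect on one participant's mean.** Let a be the mean daily score before dose #2 within the season and b the mean after it.

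Whole-season mean − post-dose mean = [d·a + (L − d)·b]/L − b = (d/L)(a − b).

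For an assumed difference of 2 to 4 points between a and b, in either direction, with d = 7:
- L = 21: 7/21 × 2 = 0.67 to 7/21 × 4 = 1.33 points.
- L = 60: 7/60 × 2 = 0.23 to 7/60 × 4 = 0.47 points.

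This is a shift in one late-dosed participant's score, not in the treatment difference. The latter depends on how many are dosed late and whether the shift differs by arm; the documents give neither.

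**4. Participants without dose #2.** Days after dose #2: 0, so the post-dose rule yields no TNSS, TOSS, TSS or DMS average. On the local-BPS wording, the CSMS average would use all L days less exclusions. The same person would then have a CSMS average but no averages for its components.

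**5. Pollen covariate.** Table 3 places BPS and peak BPS in one row with one covariate, and Appendix 14.1 repeats it. Unlike items 1 to 3, this applies to every participant in the peak analysis, whatever the timing of dose #2. If peak and whole-season averages were exactly linearly related across pollen sites, the adjusted comparison would not change; otherwise some precision is lost.

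**The case against.** The strongest reply is that SAP 7.1 does set one window. The DMS paragraph speaks of daily e-diary scores in general, and SAP 11.1 includes daily TSS and daily CSMS when it lists such scores. Table 3 also groups all five as field scores from the e-diary. On this view the CSMS sentence adds only that the season is the participant's local one. This reading is plausible. A reader might infer that CSMS is clearly averaged over the whole season while its components are not; the documents do not support that. They support an ambiguity.

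A reader might also infer that never-redosed participants have no usable data and that a planned analysis cannot be run. That goes too far. SAP 7.2.2 says such analyses may be done, and Appendix 14.1 names one only for titrated SPT. Titrated SPT, the peak-season EEU scores and RQLQ(S) do not use the post-dose diary rule, and on the local-BPS reading CSMS is computable too. What stands is narrower: if the analysis is extended to diary scores, TNSS, TOSS, TSS and DMS have no defined window for these participants.

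It can further be said that the objective concerns dose #2, that everyone in FAS-B received it, and that SAP 7.2.2 lists a possible subgroup by dosing before or after season start. All true. But a subgroup that uses the post-dose average does not show what the all-season average would have been.

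Finally, one might want the pollen covariate recomputed for each participant over post-dose, non-travel days. That would make it depend on dose timing and travel, both after randomisation. The gain is debatable, and it is not recommended here.

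**Conclusion.** The point holds as a correctable gap in specification. The SAP's averaging rule departs from the stated endpoint for participants dosed after season start, the departure is not listed, and CSMS is left open to two readings. The largest loss per affected participant is about 7 season days. The 33% to 12% range rests on assumed season lengths, and the 47% of peak days is a worst case that also needs the peak to open the season. For participants dosed before the season, the score windows agree.

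For never-redosed participants the post-dose rule leaves no average for four of the five scores, so the optional analysis cannot check selection into FAS-B on those scores. The whole-season covariate for peak scores is a question of precision; no bias has been shown.

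All of this concerns Part B secondary endpoints outside the six-step hierarchy in SAP 8.2. The Part A primary analysis is unaffected.

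**What to change.** 1. State one averaging window for TNSS, TOSS, TSS, DMS and CSMS, worded identically in SAP 7.1 and Table 3. If the post-dose-2 window is kept for FAS-B, list it in SAP 1.4 and also report the all-BPS-days average, which is the protocol endpoint.
2. State that the analysis irrespective of dose #2 will be performed for the diary scores, using all BPS diary days for every participant less the EEU-day exclusions, and add it to the diary row of Appendix 14.1.
3. For the peak-BPS endpoints, use the local average pollen count over the peak BPS as the covariate.

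Diary entries and daily pollen counts are already collected. The cost is SAP wording, a little extra programming and one additional supportive table.
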